5.4 Inclusion/Exclusion Criteria

The inclusion and exclusion criteria for the veteran participants will be based on the telephone screen and preliminary assessment procedures specified previously. These procedures will be used to form the 4 participant groups and to insure that the participants can complete the tasks (See Table 1 above). All of the participants will be aged 20 to 50 years, have normal or near normal audiometric test results, corrected or uncorrected vision of 20/30 or better, and no evidence of hyperacusis. The mTBI-only group will have a history of blast exposure, evidence of possible brain injury, no significant symptoms consistent with PTSD, but elevated hearing handicap scores on

the Hearing Handicap Inventory for Adults (HHIA). The mTBI+PTSD group will have a history of blast exposure, evidence of possible brain injury, significant symptoms consistent with PTSD, and elevated hearing handicap scores on the HHIA. The PTSD-only group will have no history of blast exposure or brain injury but they will have significant symptoms consistent with PTSD. The Normal control group will have no history of blast exposure or brain injury, and little or no symptoms of PTSD (or other psychiatric disorder) or hearing handicap. All of the veteran participant must not have a history of hearing aid use, or brain injury or disease more severe than that targeted by the study. In addition, the veteran participants must be able to be paid for their participation.

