5.6 Data Analysis

Part 1 Analysis

Preliminary Analyses - The analysis will begin with basic descriptive statistics including means and standard deviations for continuous data and examination of distributional assumptions for all study measurements including the questionnaire data (e.g., HHIA, WHODAS-II, SSQ and HHIA-SO) for each group of interest. These analyses will be used to evaluate the extent of missing data and to identify outliers.

Primary Analyses - Random Forests (RF, Breiman, 2001) will be applied to determine which auditory, language processing, and executive function variables best discriminate the three groups. This technique performs variable selection and the variables are ranked by Gini score, a measurement of average accuracy of all trees containing a particular variable. One-way ANOVA will be used to determine differences between groups for normally distributed continuous data. Analysis of covariance (ANCOVA) will be used to adjust for differences between groups. If assumptions for the parametric test are not met, a non-parametric alternative will be used (e.g., Kruskal-Wallis, non-parametric ANCOVA). The p-values will be adjusted for multiple testing by using a false discovery rate method whenever more than one variable is being tested. Statistical assumptions (e.g., linearity, normality) will be verified prior to hypothesis testing. All statistical analyses will be two sided and the significance level will be 0.05.

Sample Size and Power - A sample size of 117 per veteran group will achieve 80% power at a 0.05 significant level to detect an effect size (i.e., odds ratio) of 2.50. This sample size was computed based on an adjustment that was made assuming that a multiple regression of the independent variable of interest on the other independent

variables in the model will result in an R-squared of 0.20. For one-way ANOVA, the total sample of 468 subjects achieves 80% power to detect an effect size of 0.18 or larger with a two-sided significance of 0.01 to account for multiple hypotheses testing. For analysis of covariance, the study is powered (0.80) to detect an effect size of 0.16 assuming the strength of the relationship between the response of interest and the covariates, measured as R-squared, is 0.20.

Part 2 Analysis

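### The Part 1 ANCOVA detectable effect of 0.16 is a best case: it assumes covariates unrelated to group, while the ANCOVA is there to adjust for group differences

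*Combined protocol and SAP*

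**What the plan says.** Section 5.6, Part 1, Primary Analyses, gives the ANCOVA its role: "Analysis of covariance (ANCOVA) will be used to adjust for differences between groups". No covariates are named.

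The Sample Size and Power paragraph of the same part gives three figures:

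- An odds ratio of 2.50 with 117 per group. This figure carries an R-squared of 0.20 among predictors; the phrase used is "assuming that a multiple regression of the independent variable of interest on the other independent".
- An ANOVA figure: "For one-way ANOVA, the total sample of 468 subjects achieves 80% power to detect an effect size of 0.18 or larger". The alpha there is 0.01, chosen as an allowance for multiplicity.
- The ANCOVA figure: "For analysis of covariance, the study is powered (0.80) to detect an effect size of 0.16 assuming the strength of the relationship between the response". That relationship is then put at an R-squared of 0.20. The sentence states no alpha and no R-squared between group and covariates.

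Section 5.4 says of the telephone screen and preliminary assessments: "These procedures will be used to form the 4 participant groups". Table 1 in section 5.1 shows what they sort on: blast history, evidence of brain injury, PCL-M score and hearing handicap. Part 1 has no randomisation.

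**The concern.** A covariate changes the precision of a group comparison in two ways. It removes residual variance, which helps. If it is related to group, it also takes away part of the information about the group contrast, which hurts. Under randomisation the second effect is negligible in expectation. In Part 1 it cannot be assumed away, because a covariate brought in because the groups differ on it is related to group by construction.

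The move from 0.18 (ANOVA) to 0.16 (ANCOVA) credits the first effect. The question is whether it charges anything for the second. If it does not, the adjusted comparisons, which are among the primary analyses, are described as more sensitive than this design will generally make them. A reader could then take a null adjusted difference near f = 0.16 as coming from an analysis with 80% power when the power was lower.

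**Working it through.** **Inputs.** N = 468 in 4 groups of 117 (sections 5.1 and 5.6). Response-covariate R-squared 0.20 (ANCOVA sentence). Alpha 0.01 (ANOVA sentence; the ANCOVA sentence gives none). The group-covariate R-squared, written R²g below, is not in the documents and is varied as an assumption.

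**Formula.** Noncentral F with 3 and 463 degrees of freedom (one covariate; using none or five makes no material difference) and noncentrality

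λ = N × f² × (1 − R²g) / (1 − R²),

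where R² is response on covariates and R²g is the share of the tested group contrast explained by the covariates.

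**Reproducing the plan.**

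- ANOVA (R² = R²g = 0): power at f = 0.18 is 78.3%; 80% power is reached at f = 0.1829, which rounds to the stated 0.18.
- ANCOVA (R² = 0.20, R²g = 0): 0.1829 × √0.80 = 0.1636, which rounds to the stated 0.16. At exactly f = 0.16, λ = 468 × 0.0256 / 0.80 = 14.98 and power is 77.6%.

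The other settings tried do not give 0.16. Alpha 0.05 with four groups gives 0.137. Alpha 0.01 with three groups gives 0.179 (N = 351) or 0.155 (N = 468). Alpha 0.01 with four groups and R²g = 0.20 gives 0.183. The stated figure is therefore the ANOVA figure with 20% of the residual variance removed and no charge for overlap with group.

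**Adding the overlap.** Alpha 0.01, R² = 0.20, imbalance fully aligned with the tested contrast. Detectable f is 0.1636 / √(1 − R²g). The last column translates R²g into a covariate difference between the two blast and the two non-blast groups, 2 × √(R²g / (1 − R²g)) within-group SDs.

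| R²g (assumed) | Power at f = 0.16 | Detectable f at 80% | Covariate difference |
|---|---|---|---|
| 0 | 77.6% | 0.164 | 0 |
| 0.05 | 74.7% | 0.168 | 0.46 SD |
| 0.10 | 71.6% | 0.172 | 0.67 SD |
| 0.20 | 64.4% | 0.183 | 1.0 SD |

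At R²g = 0.20 the factors (1 − 0.20) and 1/(1 − 0.20) cancel, so the detectable effect returns to the unadjusted ANOVA value.

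**Simulation check** (6,000 runs, 4 × 117, one covariate, effect set as blast versus non-blast, f = 0.16). With no overlap, power was 77.8%. With aligned overlap it was about 72% at R²g 0.10 and 63.6% at 0.20. With the covariate shift orthogonal to the effect it was 77.2% at 0.10 and 77.7% at 0.20, so there was no loss.

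**Rounding.** Part of the gap from 80% comes from rounding 0.1636 to 0.16 (80.0% against 77.6%, or 2.4 points). Starting from 0.1636, an aligned R²g of 0.20 takes power from 80.0% to 67.2%.

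**The case against.** **The figure is not miscalculated.** This stands. The 0.16 reproduces under a condition that the sentence only half states. The fault is an unstated assumption that conflicts with the analysis's purpose, not an arithmetic slip.

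**The 0.20 overlap is not the plan's.** This also stands. A reader might infer that the paragraph applies a group-covariate R-squared of 0.20 to the odds ratio and then leaves it out of the ANCOVA. The documents do not support that. The 0.20 belongs to the odds-ratio calculation alone, the model behind that odds ratio is not described, and nothing says that its independent variable of interest is group membership. It could be a correlation among test measures.

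**The largest loss needs a large, aligned imbalance.** An R²g of 0.20 is about a full SD between blast and non-blast groups. Eligibility narrows some obvious covariates: everyone is aged 20 to 50 with normal or near-normal audiometry. Averaged over directions at R²g 0.20, power is about 74%. This rules out 64% as a headline but does not restore 0.16 as the expected value.

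**Alpha is uncertain.** Section 5.6 also says "All statistical analyses will be two sided and the significance level will be 0.05", with false discovery rate adjustment. At alpha 0.05, power at f = 0.16 would be 91.4% with no overlap and 83.6% at an aligned 0.20. But alpha 0.05 does not reproduce the stated 0.16, so the planning figure evidently rests on 0.01, and the sentence should say so.

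**Little hangs on it.** The 117 per group is tied to the odds ratio, and the plan sets no rule for reading null results. That limits the consequence, but the stated sensitivity is still wrong for general use.

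**Conclusion.** The point holds in a limited form. The 80% power for f = 0.16 is what this ANCOVA would deliver, apart from rounding, if its covariates were unrelated to group. The plan uses it where that condition is not expected to hold, and no other passage supplies the missing term. Over an assumed R²g of 0 to 0.20, the detectable effect runs from about 0.16 to about 0.18. At the upper end, adjustment gains nothing over the one-way ANOVA.

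This rests on alpha 0.01, a response-covariate R-squared of 0.20, an assumed R²g, and full alignment of the imbalance with the tested contrast. It would go too far to say that the ANCOVA has 64% power: that value belongs to one assumed overlap in the least favourable direction, and the documents give neither the overlap nor the direction. The design and the sample size are not called into question.

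**What to change.** Replace the ANCOVA sentence in section 5.6, Part 1, Sample Size and Power, with wording such as:

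*For analysis of covariance at a significance level of 0.01, with an R-squared of 0.20 between response and covariates, the effect size detectable with 80% power is about 0.16 if the covariates are unrelated to group. It rises to about 0.18 if an assumed group-covariate R-squared of 0.20 is fully aligned with the group difference being tested. Adjustment is therefore not presumed to improve on the one-way ANOVA figure of 0.18.*

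Label the 0 to 0.20 range as an assumption, and do not present 0.20 as carried over from the odds-ratio calculation. Naming the intended covariates in the Primary Analyses text would let a reader judge where in the range the study is likely to fall.

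The cost is one rewritten sentence and a slightly less favourable stated sensitivity. The sample size stays at 117 per group, and no analysis, visit or procedure changes.

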Standardized fitting and verification procedures consistent with the American Academy of Audiology guidelines for audiology management of adult patients will be used. The hearing aids will be obtained through the VA hearing aid procurement procedures because the participants qualify for hearing aids due to their auditory impairment. High-end behind-the-ear hearing aids (Phonak Bolero Q90) will be fitted binaurally. The hearing aids will provide mild gain with high-frequency emphasis, which will be verified acoustically with real ear measures. The noise suppression circuitry of the hearing aids will be activated but the frequency compression or shifting will be deactivated.

Additionally, to reduce the risk of sounds being too loud for the participants, Maximum Power Output will be set below the loudness discomfort levels of the participants.

Prior to their hearing aid fitting the participants in the two treatment groups will complete the unaided portion of the Abbreviated Profile of Hearing Aid Benefit (APHAB, Cox & Alexander, 1995), along with the HHIA, and SSQ as pretreatment measures of self-perceived hearing handicap, and situational hearing skills. To assess pre-fitting speech perception and language processing the California Consonant Test (CCT; Owens & Schubert, 1997) will be administered in the sound field at 65 dB HL in quiet and with multi-talker babble.

Recovery of co-articulation (phonetic context effect) will be measured with a vowel identification task. The vowels will be presented in the context of /d/ and /b/ sounds (Holte & Lotto, 2006). The extent to which the consonant context changes the perception of vowel categories will be measured.

As in Part 1 of the study, sentence level processing will be measured with the auditory and reading versions of subtests 1 through 10 from the Computerized Revised Token Test (CRTT and CRTT-R respectively) and will be administered in quiet and in babble to assess sentence level processing in both auditory and reading domains in optimal and adverse acoustic conditions.

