Follow-up Testing – The participants will be followed over a 6-month period. One week (+/- 3 days) after the fitting the participants will be seen in the lab to re-verify the fit of their hearing aids and to determine any problems. The hearing aid use-time will be recorded from the data-logging system of the hearing aids as a reflection of hearing aid benefit and to document the extent to which the participants are wearing their hearing aids. During this session, both the aided and unaided portions of the APHAB will be administered along with the International Outcomes Inventory for Hearing Aids (IOI-HA; Cox & Alexander, 2002). In addition, the participants will answer a single question about their likelihood to continue hearing aid use. Intent to continue use tends to be related to user satisfaction with commercial products and service provision in other areas of healthcare. The participants also will complete the HHIA, and SSQ. The CCT, CRTT, CRTT-R and the phonetic context effect tasks will be re-administered with and without hearing aids.

Home Visits – The participants will be visited in their homes by study staff at three different times: 1-, 2- and 4-months post-fitting (+/- 1 week). The home visits will occur to reduce participant burden and encourage retention. However, some participants might prefer to be seen in the lab or clinic than their homes, and if that is the case those participants will be accommodated. Hearing aid use-time will be recorded from the data-logging system of the hearing aids and the hearing aids will be checked to determine appropriate function. During these visits the HHIA, SSQ, APHAB, IOI-HA, and the intent to continue use question will be re-administered. New hearing aid batteries will be provided and participants will be encouraged to wear their hearing aids for longer periods of time if their use-time is below 8 hours a day. At 6-months post-fitting (+/- 1 week) the laboratory follow-up testing will be repeated.

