Delayed-Treatment Control Group – The participants in the delayed-treatment control group will be selected from the mTBI-only group and followed over a 12-month period (+/- 2 weeks). At the onset of Part 2 they will complete the HHIA, SSQ, and the unaided portion of the APHAB. They will complete the speech perception and language tasks administered to the treatment group (CCT, phonetic context effect, and CRTT tasks) but unaided only. The delayed-treatment groups will receive home visits at 1, 2, 4 months (+/- 1 week) post-entry, at which times they will complete the HHIA, SSQ, and the unaided portion of the APHAB. At 6 months post-entry their pure tone hearing thresholds will be measured to determine possible changes in hearing sensitivity, and the procedures used with the treatment groups will be applied with the same sequence of follow-up sessions.

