5.5 Study Evaluations

All of the evaluations to be conducted are listed above under study procedures (5.1). The data will be collected by the investigators and study staff. The types of assessment methods vary and include questionnaires, review of records, behavioral tests, and physiological procedures. Some data will be acquired via computer, while others will be administered face to face and via paper-and-pencil.

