Primary Analyses – Basic descriptive statistics will be computed and examination of statistical assumptions will be performed for all study measurements. For questionnaire data, analysis of variance (ANOVA) or Kruskal Wallis test will be used to determine differences in the overall and subset scores between the mTBI groups. The analysis will also include basic descriptive statistics for behavioral data test measures at baseline and at 6 months for the mTBI-only and mTBI+PTSD groups, and at baseline and 12 months for the delayed-treatment groups. We will focus on the changes in the behavioral test measures from baseline to 6 months (mTBI-only and mTBI+PTSD treatment groups) and from baseline to 12 months (delayed-treatment groups). Specifically, paired t-test or Wilcoxon signed rank test will be used to determine change at 6 or 12 months and this test will be applied to each behavioral test measure separately. False discovery rate will be used to adjust the p-values for multiple hypotheses testing. All statistical analyses will be two sided and the significance level will be 0.05.

Secondary Analyses – For longitudinal analysis, the data will be modeled using linear-mixed models for which the outcome is the behavioral test measure across time. The predictors will include time, group and interaction between group and time. Covariates will be added to the model as needed. In addition, variables with a high Gini score from Part 1 will be correlated with final hearing aid results as a preliminary investigation of whether hearing aid benefit can be associated by any of the variables obtained above. We will measure correlations using either Pearson's or Spearman's correlation coefficient. We will adjust the p-values for multiple testing by using a false discovery rate method whenever more than one variable is being tested. Single-subject design metric also will be used to investigate individual responses to the hearing aid treatment.

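### Part 2 collects HHIA and SSQ repeatedly in fitted and not-yet-fitted groups, but specifies no longitudinal group comparison for them

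*Combined protocol and SAP*

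**What the plan says.** **Analysis.** Section 5.6 (Part 2, Primary Analyses) states: "For questionnaire data, analysis of variance (ANOVA) or Kruskal Wallis test will be used to determine differences in the overall and subset scores", the comparison being between the mTBI groups. No visit, change score, baseline covariate or within-person term is given. The paired tests in the same paragraph are for the behavioural measures. The Secondary Analyses paragraph specifies "linear-mixed models for which the outcome is the behavioral test measure across time", with time, group and their interaction as predictors. Section 5.5 treats questionnaires and behavioural tests as different things: "The types of assessment methods vary and include questionnaires, review of records, behavioral tests, and physiological procedures".

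**Questionnaire schedule (section 5.1, Part 2 Procedures).** The treatment groups complete the unaided APHAB before fitting, "along with the HHIA, and SSQ as pretreatment measures of self-perceived hearing handicap, and situational hearing skills". At one week, "The participants also will complete the HHIA, and SSQ". At the home visits in months 1, 2 and 4, "During these visits the HHIA, SSQ, APHAB, IOI-HA, and the intent to continue use question will be re-administered". The laboratory follow-up is repeated at month 6. The delayed-treatment groups complete HHIA and SSQ at entry and have visits at months 1, 2 and 4, "at which times they will complete the HHIA, SSQ, and the unaided portion of the APHAB". From month 6 they follow the treatment groups' procedures.

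**Behavioural schedule.** In the treatment groups the consonant, phonetic-context and token tests are given before fitting, at one week and at six months. In the delayed groups they are given at entry and then in the sequence that starts at month 6. Neither arm has them at months 1, 2 or 4.

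**The concern.** The model built for repeated measurement is assigned to the outcomes with fewer visits. The outcomes measured most often get a test that takes one score per person.

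Specific question d in section 3.0 asks both whether veterans perceive benefit and whether they demonstrate it. The first half rests on the questionnaires. Section 5.2 assigns participants at random to treatment or delayed treatment, so the months before the delayed groups are fitted allow a concurrent comparison of fitted with unfitted participants. The primary behavioural analysis is a set of within-group paired tests, which makes this comparison more valuable.

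As written, the analyst must choose one questionnaire visit without guidance, and the other visits add nothing to any specified group comparison. In a study of 25 per group that is a substantial loss of information.

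**Working it through.** **1. The plan's own figure.** The Part 2 power statement gives four groups of 25, alpha 0.01, power 0.80 and detectable f = 0.38. With noncentral F, λ = N·f² = 100 × 0.1444 = 14.44 on 3 and 96 degrees of freedom, power is 73%. Power of 80% needs f of about 0.405. The stated figure does not reproduce for four groups. That is a separate matter on which this point does not depend. What matters here is that the statement counts 100 participants, one score each, and uses no repeated visits.

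**2. Inputs for the fitted-versus-unfitted comparison.** n = 50 per arm (two strata of 25, from section 5.2) and alpha 0.01 two-sided (from the power statement). Assumptions, because the documents give no values: standardised difference d = 0.5, constant over visits, and equal correlation ρ between any two scores from one person, including the entry score.

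**3. Formula.** Power comes from noncentral t with about 98 degrees of freedom and δ = (d/√V)·√(n/2) = 5d/√V, where V is the variance relative to one unadjusted score:

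- one visit, unadjusted: V = 1
- one visit, entry-adjusted: V = 1 − ρ²
- mean of months 1, 2 and 4, unadjusted: V = (1 + 2ρ)/3
- mean of months 1, 2 and 4, entry-adjusted: V = (1 + 2ρ)/3 − ρ²

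With one unadjusted visit, δ = 2.5 and power is 45%.

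| ρ | one visit, adjusted | three visits, unadjusted | three visits, adjusted: V | δ | power |
|---|---|---|---|---|---|
| 0.3 | 50% | 79% | 0.443 | 3.76 | 87% |
| 0.5 | 60% | 67% | 0.417 | 3.87 | 89% |
| 0.7 | 81% | 57% | 0.310 | 4.49 | 97% |
| 0.8 | 94% | 53% | 0.227 | 5.25 | over 99% |

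The move from 45% to the last column combines two gains. At low ρ most of it comes from the repeated visits, and at high ρ most comes from the entry score. Using both is best at every ρ tried.

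**4. If the effect builds up slowly.** Assume 40%, 60% and 80% of the month-6 effect at months 1, 2 and 4, with a month-6 d of 0.5 and ρ = 0.5. The average effect over the three visits is 0.5 × 0.6 = 0.30.

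- Unadjusted: δ = 5 × 0.30/√0.667 = 1.84, power 22%, against 45% for month 6 alone.
- Entry-adjusted: δ = 5 × 0.30/√0.417 = 2.32, power 39%, against 60% for month 6 alone (δ = 2.5/√0.75 = 2.89).
- Entry-adjusted mean of months 1, 2, 4 and 6: average effect 0.35, V = (1 + 3 × 0.5)/4 − 0.25 = 0.375, δ = 5 × 0.35/√0.375 = 2.86, power 59%.

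An average that leaves out month 6 can therefore lose power. An average that includes it roughly breaks even under this build-up.

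**5. Is month 6 a concurrent comparison?** The treatment groups' procedures begin with HHIA and SSQ before fitting, and the delayed groups enter those procedures at month 6. The treated participants complete both instruments at their own month-6 visit. Read together, these passages give a month-6 score in fitted and not-yet-fitted participants. The protocol does not say this in one place.

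**The case against.** **Part 2 is preliminary.** Section 5.2 says that it is not a randomised controlled trial, and those who opt out are replaced. That limits how strongly any contrast can be interpreted. It does not explain why the most frequently measured outcomes have no longitudinal analysis, since Part 2 does specify tests, multiplicity control and power.

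**The visits are not wholly unused.** A reader might infer that the home-visit questionnaires are discarded. The documents do not support that: descriptive statistics cover all study measurements, and the single-subject metric could use the series. Neither is a longitudinal comparison of groups, so the narrower point stands.

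**Inflated false positives.** A reader might also infer that all visit scores will go into the ANOVA as independent observations, raising the type I error. Nothing in section 5.6 proposes this, and the power statement counts participants, 25 per group. The supportable criticism is an unnamed visit and an unspecified longitudinal analysis.

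**The gain is assumption-bound.** This stands. ρ, d and a constant effect are all assumed. The Treatment Options rationale in section 2.0 (perceptual learning, central reorganisation) makes a gradual effect plausible, so the month-6 contrast belongs in the fix.

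**Group structure.** Section 5.1 draws the delayed group from the mTBI-only participants, whereas section 5.2 has delayed groups in both strata. The 50-against-50 figures rest on section 5.2. The two passages must be reconciled, but the mismatch between schedule and analysis exists under either.

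**Conclusion.** The point holds as a gap in specification. HHIA and SSQ have repeated, concurrent scores in fitted and unfitted groups, and the plan directs them to a one-score group test while reserving its mixed model for measures absent from months 1, 2 and 4. No false-positive inflation follows from the text.

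Under the stated assumptions, power rises from 45% with one unadjusted visit to between 87% and over 99% with three entry-adjusted visits. Against one entry-adjusted visit the starting point is 50% to 94%, so the part due to the repeated visits alone shrinks as ρ rises. The direction is the same at every ρ examined if the effect is constant, but can reverse for an average without month 6 if the effect builds up slowly. This is an inexpensive improvement that should be made; the gap does not invalidate Part 2.

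**What to change.** In section 5.6 (Part 2), extend the planned linear mixed model to HHIA and SSQ, total and subscales:

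- Outcomes: scores at months 1, 2 and 4 and at month 6, taking the delayed groups' pre-fitting score at month 6. State explicitly in section 5.1 that this score is collected before fitting.
- Terms: participant random effect, Part 2 entry score as covariate, categorical visit, arm, PTSD group, arm-by-visit and arm-by-PTSD. Question d needs the last term because it asks whether PTSD influences benefit.
- Reporting: the arm contrast at month 6 and the contrast averaged over visits, with one named in advance as the main test. Keep the ANOVA or Kruskal-Wallis as descriptive.
- Reconcile sections 5.1 and 5.2 on whether there is a delayed mTBI+PTSD group, since the arm-by-PTSD term requires it.

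The cost is SAP wording and modest extra analysis. No new participants, visits or instruments are needed, provided the month-6 pre-fitting questionnaires are collected as the joint reading implies. The drawback is that the averaged contrast describes the whole period and not an endpoint, and can dilute a late effect; reporting month 6 alongside it addresses that.
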